#### 6.2.1 Downloading Site Registration Documents

Download the site registration forms from the protocol-specific page located on the CTSU members' website. Permission to view and download this protocol and its supporting documents is restricted to institutions and its associated investigators and staff on a participating roster. To view/download site registration forms:

• Log in to the CTSU members' website (**Description**) using your CTEP-IAM username and password;

- Click on *Protocols* in the upper left of the screen:
  - $\circ$  Enter the protocol number in the search field at the top of the protocol tree; or
  - Click on the By Lead Organization folder to expand, then select *Alliance*, and protocol number *A211102*.
- Click on *Documents*, *Protocol Related Documents*, and use the *Document Type* filter and select Site Registration to download and complete the forms provided. (Note: For sites under the CIRB, IRB data will load automatically to the CTSU.)

#### 6.2.2 Requirements for A211102 Site Registration

- IRB approval (For sites not participating via the NCI CIRB; local IRB documentation, an IRB-signed CTSU IRB Certification Form, Protocol of Human Subjects Assurance Identification/IRB Certification/Declaration of Exemption Form, or combination is accepted)
- Completed and signed RPFNA Training Form (see Section 6.3.4)

### 6.2.3 Submitting Regulatory Documents

Submit required forms and documents to the CTSU Regulatory Office using the Regulatory Submission Portal on the CTSU members' website.

To access the Regulatory Submission Portal log in to the CTSU members' website, go to the *Regulatory* section and select *Regulatory Submission*.

Institutions with patients waiting that are unable to use the Regulatory Submission Portal should alert the CTSU Regulatory Office immediately by phone or email:

in order to receive further instruction and support.

#### 6.2.4 Checking Site's Registration Status

Site registration status may be verified on the CTSU members' website.

- Click on *Regulatory* at the top of the screen;
- Click on *Site Registration*; and
- Enter the sites 5-character CTEP Institution Code and click on Go:
  - Additional filters are available to sort by Protocol, Registration Status, Protocol Status, and/or IRB Type.

Note: The status shown only reflects institutional compliance with site registration requirements as outlined within the protocol. It does not reflect compliance with protocol requirements for individuals participating on the protocol or the enrolling investigator's status with NCI or their affiliated networks.

#### 6.2.5 Site credentialing for RPFNA requirement

**6.2.5.1** Participating institutions must have a RPFNA Training Form (RTF) on file with CTSU. If this form has been previously submitted to CTSU it does not need to be resubmitted unless personnel updates have occurred at the enrolling site. This training form will be available on the Alliance and CTSU websites as a supporting document to the protocol.

The completed RTF is to be sent by email to

After receiving documentation of either previous approval to perform RPFNA (see

Section 6.2.5.2) or completion of training, will complete the signature line of the form and return it to the site. Site staff will then submit the form to the CTSU Regulatory Portal per Section 6.2.3.

**6.2.5.2** Sites that either have been approved for participation in CALGB 70806 or routinely perform RPFNA (> 10 RPFNA per year) do not need to undergo RPFNA training and can indicate this on the RTF.

### 6.2.5.3 **RPFNA** training

For sites that wish to undergo RPFNA training, this can consist of either 1) video training and phone conferencing with and the original or, 2) on-site training at Contact information for training is:

For sites that desire electronic training, there is a training video that can be sent and can be available either by phone or email to answer questions and provide suggestions and feedback

We have an on-site training program for any institution that is interested in performing RPFNA in the operating room and in the clinic. In our prior CALGB study testing of the reproducibility of RPFNA, all interested sites sent a team to Duke University for RPFNA training. Typically, teams sent for training included either a surgeon or a physician assistant/midlevel provider who was well skilled in breast procedures.

#### 6.3 **Patient Registration Requirements**

**Informed consent:** The patient must be aware of the neoplastic nature of her disease and willingly consent after being informed of the procedure to be followed, the experimental nature of the therapy, alternatives, potential benefits, side-effects, risks, and discomforts. Current human protection committee approval of this protocol and a consent form is required prior to patient consent and registration.

**Protected Health Information:** RPFNA and whole blood collected for this study will be sent directly to City of Hope Hospital in California. These samples will be labeled with patient initials, study ID, and collection date.

#### 6.4 **Patient pre-registration (Step 0) procedures**

The Oncology Patient Enrollment Network (OPEN) is a web-based registration system available on a 24/7 basis. OPEN is integrated with CTSU regulatory and roster data and with the LPOs registration/randomization systems or the Theradex Interactive Web Response System (IWRS) for retrieval of patient registration/randomization assignment. OPEN will populate the patient enrollment data in NCI's clinical data management system, Medidata Rave.

Requirements for OPEN access:

- A valid CTEP-IAM account;
- To perform enrollments or request slot reservations: Must be on an LPO roster, ETCTN corresponding roster, or participating organization roster with the role of Registrar. Registrars must hold a minimum of an Associate Plus (AP) registration type;
- If a Delegation of Tasks Log (DTL) is required for the study, the registrars must hold the OPEN Registrar task on the DTL for the site; and
- Have an approved site registration for the protocol prior to patient enrollment.

To assign an Investigator (IVR) or Non-Physician Investigator (NPIVR) as the treating, crediting, consenting, drug shipment (IVR only), or receiving investigator for a patient transfer in OPEN, the IVR or NPIVR must list the IRB number used on the site's IRB approval on their Form FDA 1572 in RCR. If a DTL is required for the study, the IVR or NPIVR must be assigned the appropriate OPEN-related tasks on the DTL.

Prior to accessing OPEN, site staff should verify the following:

- Patient has met all eligibility criteria within the protocol stated timeframes; and
- All patients have signed an appropriate consent form and Health Insurance Portability and Accountability Act (HIPAA) authorization form (if applicable).

Note: The OPEN system will provide the site with a printable confirmation of registration and treatment information. You may print this confirmation for your records.

Access OPEN at or from the OPEN link on the CTSU members' website. Further instructional information is in the OPEN section of the CTSU website at For any additional questions, contact the CTSU Help Desk at

#### 6.5 Central review of RPFNA samples

After pre-registration and prior to registration/randomization, RPFNA samples must be collected and shipped to **event** laboratory per Section 14.0 for determination of eligibility (cytological atypia defined as Masood score of 14-17). **Event** laboratory will report the results within 30 days (20 business days) from receipt of RPFNA specimens. The results, along with the cytology report, will be sent to the registering institution and the Alliance Pathology Coordinators at Mayo Clinic Rochester. The Alliance Pathology Coordinator will then go into the pre-approval application, mark the patient as approved or not approved. See Section 14.6.1 for an explanation of the cytology report.

If approved, the patient may be registered and randomized to the study.

#### Email Template (to be completed by

Study Number: A211102 Patient ID: Approved or Not approved: Site contact information: CRA/Study Coordinator's name: Phone number: E-mail address:

#### 6.6 Registration/Randomization (step 1) procedures

- **6.6.1** All site staff will use OPEN to enroll patients to this study. OPEN can be accessed at or from the OPEN tab on the CTSU members' side of the website at Note: The OPEN system will provide the site with a printable confirmation of registration. Please print this confirmation for your records.
- **6.6.2** Treatment on this protocol must commence at the accruing institution under the supervision of an Alliance member physician.

- **6.6.3** Study treatment cannot begin prior to registration/randomization and must begin  $\leq 14$  days after registration/randomization.
- **6.6.4** Pre-treatment tests/procedures (see Section 4.0) must be completed within the guidelines specified on the test schedule.
- **6.6.5** All pre-treatment symptoms/conditions must be evaluated and documented at baseline (see Section 10.5.1).
- **6.6.6** RPFNA results are available on site.

Note: Once the above conditions have been met, access the OPEN website and follow the instructions for registration/randomization.

#### 6.6.7 Correlative Research:

- **6.6.7.1** A mandatory correlative research component (i.e., RPFNA and blood samples) is part of this study for all patients, the patient will be automatically registered onto this component (see Sections 3, 4, and 14 of the protocol).
- **6.6.7.2** Patient has/has not given permission for coded samples and related coded information to be kept for use in future research to learn about, prevent, or treat cancer. This may also include research on inherited traits (genes passed on in families).
- **6.6.7.3** Patient has/has not given permission for coded samples and related coded information to be kept for use in future research to learn about, prevent, find or treat other health problems (for example: diabetes, Alzheimer's disease, or heart disease). This may also include research on inherited traits (genes passed on in families).
- **6.6.7.4** Patient has/has not given permission for someone from their hospital or the Alliance to contact them in the future to ask to take part in more research.

#### 6.7 Stratification factors

The stratification factors defined below will be used at the time of patient registration:

- BRCA mutation (Yes vs. No mutation or unknown).
- Prior abnormal excisional biopsy results (Yes vs. No or unknown).
- Fasting baseline insulin: (Fasting insulin > 2x ULN vs. Fasting Insulin  $\leq 2x$  ULN)

After the patient has been registered to the study, the values of the stratification factors will be recorded. The patient then will be assigned to one of the following treatment groups using the Pocock and Simon dynamic allocation procedure which balances the marginal distributions of the stratification factors between the treatment groups:

- Metformin
- Placebo

#### 6.8 **Procedures for Double-Blinding the Treatment Assignment**

After the treatment assignment has been ascertained in the OPEN application, the patient's study medication code number will be displayed on the confirmation of registration screen. If the code number is not displayed, contact the Registration Office at

The number of the treatment bottle assigned to the patient will be recorded on the Treatment Form by institutional staff.

#### 6.9 Open-label and crossover re-registration (step 2) procedures

At the time of the 12-month RPFNA visit, all patients will be unblinded per Section 7.3.

All patients who were randomized to receive metformin will be re-registered and begin receiving open-label metformin as described below.

Patients who were randomized to receive placebo and elect to cross over to open-label metformin therapy will be re-registered to receive open-label metformin as follows:

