## 3.3.2 The following laboratory values obtained $\leq$ 30 days prior to registration/randomization:

- Hemoglobin  $\ge 9 \text{ g/dL}$ .
- Absolute neutrophil count (ANC)  $\geq 1500/\text{mm}^3$
- Platelet count  $\geq$  75,000/mm^3
- Creatinine  $\leq 1.4 \text{ mg/dL}$
- Total bilirubin  $\leq 3.0 \text{ mg/dL}$
- Aspartate transaminase (AST)  $\leq 3$  x upper limit of normal (ULN)
- Alanine transaminase (ALT)  $\leq$  3 x ULN
- **3.3.3** Negative pregnancy test done  $\leq$  7 days prior to registration/randomization, for women of childbearing potential only.

A female of childbearing potential is a sexually mature female who: 1) has not undergone a hysterectomy or bilateral oophorectomy; or 2) has not been naturally postmenopausal for at least 12 consecutive months (i.e., has had menses at any time in the preceding 12 consecutive months).

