| Mandatory Research Blood
Draw (see Section 14.0) R          |   | $X^7$   |                              | X                                        |  |
| Patient-reported knowledge
of the arm to which they
were randomized |   |   |                              | X                                       |  |

\* The ramp-up period occurs during the first 4 weeks of blinded treatment and during the first 4 weeks of open-label treatment for patients who cross over from placebo to metformin.

\*\* Prior to the 12-month clinic visit, the CRA must call the Alliance Registration Office [contact]) to unblind the patient's treatment assignment. Patients who were receiving placebo are eligible to crossover to metformin treatment (see Section 6.8).

+/- 3 weeks for Month 6 visit; +/- 30 days for Month 12, 24, and 36 visits.

1. For women of childbearing potential only. Must be done  $\leq$ 7 days prior to registration/randomization.

2. Baseline mammogram must have been done within 365 days of pre-registration. Mammographic screening should be continued as part of the patient's regular medical care.

 See Section 14.0 for information regarding available RPFNA kits and RPFNA sample submission instructions. See Appendix II for RPFNA collection instructions. Following RPFNA, submit the RPFNA Procedure Documentation Form, available at the Alliance and CTSU A211102 study-specific web pages.

4. RPFNA at 12 months and 24 months ONLY. RPFNA at 24 months is optional for patients who were randomized to placebo and opted not to continue protocol treatment after 12 months.

5. At completion of 4 week ramp-up (phone).

6. The Patient Medication Diary will be provided for each patient for the ramp-up period. Telephone contact will be made with the patient at the end of the ramp up period to assess compliance and adverse events.

7. Blood collections (EDTA whole blood and serum samples) must be collected Monday-Thursday ONLY.

8. Pre-treatment RPFNA specimens must be submitted immediately following pre-registration (see Sections 6.6 and 14.0).

- 9. CRA or provider will make a follow-up phone call the day following the RPFNA to check in with the participant and review any side effects of the procedure (see Appendix V).

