#### **Patient re-registration steps:**

- Log into the OPEN registration system and select the appropriate patient.
- Select the next registration step.
- Complete OPEN Enrollment Form for the patient to be registered to the open-label arm.
- Enter Cycle # of the last treatment received during blinded treatment, as well as the stratification factors, on the OPEN Enrollment Form.
- Once the open-label registration has been successfully completed confirmation will be displayed in OPEN.

If assistance is needed with this process, contact the Alliance Registration Office.

Following re-registration, open-label metformin should be ordered per Section 15.1.8.

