#### 7.3 Crossover

During the first 12 months of treatment, patients will not be unblinded except in cases of emergencies (see Section 7.5)

**Prior to the patient's 12 month clinic visit**, the CRA must call the Alliance Registration Office to find out which study agent the patient is receiving.

- 7.3.1 Patients who were receiving metformin will be re-registered to receive open-label metformin.
- 7.3.2 Patients who were receiving placebo are eligible to cross over to metformin therapy.

If the patient was receiving placebo, the CRA must contact her and ask her if she wishes to

- 1) receive metformin 850 p.o. bid for 12 mos. (including 4-week ramp-up of 850 mg p.o. qd) or
- 2) discontinue protocol therapy.

If the patient wishes to crossover to metformin therapy, the CRA will then re-register the patient per Section 6.9 and to receive open label metformin, and the patient will be administered the drug as outlined in Section 7.1.2.

**Patient Monitoring:** The Patient Medication Diary will be provided for each patient who crosses over from placebo to open-label metformin to be completed during the ramp-up period and telephone contact will be made with the patient one month +/- 3 days after crossover to assess compliance, toxicity, and to ensure the patient has increased medication to twice daily. (The diary is intended only as a tool to assist patients in adjusting to full dose at the correct time after starting study treatment.) A record of the telephone contact will be made on the Nurse/CRA Phone Contact Guide (see Appendix IV). Any problems identified will be communicated to the responsible Investigator.

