- **15.1.5 Pharmacokinetic information:** The time to peak serum level for the immediate release product is 2 to 3 hours. The onset of action is within days, with maximum effects up to two weeks. Metformin is negligibly bound to plasma proteins. Metformin is excreted in the urine, with 90% as unchanged drug. It does not undergo hepatic metabolism. Renal clearance is approximately 3.5 times greater than creatinine clearance, which indicates that tubular secretion is the major route of elimination. Bioavailability while fasting is 50% to 60%. Half-life elimination in plasma is 4 to 9 hours.
- **15.1.6 Potential Drug Interactions:** Concomitant use of the following agents may cause hyperglycemia: thiazides, other diuretics, corticosteroids, phenothiazines, thyroid products, estrogens, oral contraceptives, phenytoin, nicotinic acid, sympathomimetics, calcium channel blockers, and isoniazid. Metformin may interact with highly protein bound drugs (salicylates, sulfonamides, chloramphenicol, probenecid). Concurrent use of other glucose-lowering agents may cause hypoglycemia. Fluoroquinolones and antidiabetic agents have been reported to cause blood glucose changes. Beta blocking agents present a minimal risk of altering glucose control in nondiabetic individuals, although severe hypoglycemia has been reported with at least one beta blocking agent. Concurrent use of metformin is contraindicated in participants receiving intravascular iodinated contrast media due to an association with lactic acidosis and acute renal failure.

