- **15.1.7 Known potential toxicities:** Metformin is considered to have a favorable safety profile in diabetes mellitus patients. In a US double-blind clinical trial for patient with type 2 diabetes, gastrointestinal symptoms such as diarrhea, nausea and vomiting, abdominal discomfort, flatulence, indigestion, and asthenia were the most common reactions to the drug. These symptoms were dose-dependent, transient, and resolved spontaneously with continued use. The drug may cause GI upset so should be taken with food. Additional adverse reactions reported in 1 to 5% of subjects were abnormal stools, hypoglycemia, myalgia, lightheadedness, dyspnea, nail disorder, rash, increased sweating, taste disorder, chest discomfort, chills, flu syndrome, flushing and palpitation. A recently published trial of patients with type 2 diabetes mellitus reported a vitamin B12 deficiency with long term treatment. Lactic acidosis is a rare, but serious, metabolic complication that can occur due to metformin accumulation during treatment. Reported incidence of lactic acidosis in patients with significant renal insufficiency.
- **15.1.8 Drug procurement:** Metformin Hydrochloride 850 mg tablets will be purchased for use in the trial. Placebo tablets that are similar in size and color will also be purchased. The metformin and placebo tablets will be bottled and labeled by Pharm Ops, Inc. The bottles will be labeled so that study participants, caregivers, and investigators are blinded to the contents.

Blinded metformin/placebo: Patient-specific supplies of metformin/placebo will be ordered by the registering institution after each patient is enrolled to the study.

Fax or email the Alliance A211102 Drug Order Form to:

Patients will need to return to the clinic to receive additional supplies of blinded drug at 3, 6, and 9 months after registration. Sites may dispense a 6 month supply. However, sites that dispense a 6 month supply will be responsible for reconciliation of all medication returns. Institutional staff will contact the Registration Office for a study medication code number. Drug orders for these additional supplies should be submitted at least one week prior to each of these visits using the Alliance A211102 Drug Order Form.

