#### **15.1.9 Nursing Guidelines:**

- Metformin can have numerous drug to drug interactions that can cause either hyper or hypoglycemia. Assess patient's concomitant medications (including OTC) and instruct patients not to start any new medications while on the study without checking with the study team.
- Warn patients of gastrointestinal side effects when initially starting agent, including diarrhea, nausea, abdominal discomfort, flatulence, indigestion and vomiting. Agent should be taken with food to minimize these side effects.
- There is a rare but serious risk of lactic acidosis. Instruct patients to report nausea or weakness. Patient with these symptoms should have their electrolytes checked and/or corrected under the direction of the physician.
- Drug may cause hypoglycemia. Instruct patients in the signs and symptoms of hypoglycemia and to seek medical attention if they experience these.
- Instruct patients that if they need to have any procedure (i.e. CT scan with contrast) with iodinated contrast they must discontinue metformin per institutional practice prior to the procedure and must not resume it until their creatinine level is satisfactory (per institutional practices).

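### Step 2 states no creatinine threshold and no repeat pregnancy test before a placebo woman's first metformin dose at crossover (minor, safety only)

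*Combined protocol and SAP*

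**What the plan says.** All references are to the combined protocol and SAP.

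- **Step 1 (3.3.2, 3.3.3).** Creatinine must be at most 1.4 mg/dL within 30 days before randomization. For women of childbearing potential the criterion is "Negative pregnancy test done" no more than 7 days before randomization.
- **Step 2 (6.9, 7.3).** "Patients who were randomized to receive placebo and elect to cross over to open-label metformin therapy will be re-registered". The listed steps are selecting the patient in OPEN, completing the enrollment form, entering the last blinded cycle and stratification factors, and receiving confirmation. Then: "Following re-registration, open-label metformin should be ordered per Section 15.1.8". Section 7.3 makes every placebo patient eligible and asks only what she wishes to do.
- **New exposure (7.3).** The crossover regimen is to "receive metformin 850 p.o. bid for 12 mos. (including 4-week ramp-up of 850 mg p.o. qd"), with a fresh medication diary and a phone call.
- **Test schedule (4.0).** The chemistry panel, including creatinine, is marked at entry and at months 6, 12 and 24. The pregnancy test is marked once, before randomization. Visit windows are +/- "3 weeks for Month 6 visit; +/- 30 days for Month 12, 24, and 36 visits".
- **Drug information (15.1.5, 15.1.7).** "Metformin is excreted in the urine, with 90% as unchanged drug". "Lactic acidosis is a rare, but serious, metabolic complication that can occur due to metformin accumulation during treatment".
- **Existing safeguards.** Menstruating women must use reliable birth control at entry (3.1.7). Study medication stops if a patient becomes pregnant (13.3). Section 1.3.7 calls metformin safe in pregnancy.

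**The concern.** The protocol requires two checks before a woman may receive study drug. For the metformin arm they fall within weeks of the first metformin dose. For the placebo arm they also precede study drug, but that drug is placebo. Her first metformin dose comes about a year later, and the step-2 text does not repeat either check.

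The stake is participant safety. Metformin is cleared by the kidney, and the protocol's own drug section names accumulation as the route to its most serious toxicity. On pregnancy, the plan tests before randomization and withdraws the drug from a woman who becomes pregnant, but does not test before this first exposure. Following 6.9 and 7.3 to the letter, a site could start a woman whose renal function had worsened since entry, or who had an unrecognized pregnancy, without departing from those sections.

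**Working it through.** **1. Does any other section supply the missing condition?**

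| Section | Content | Supplies a step-2 condition? |
|---|---|---|
| 4.0 | Month-12 creatinine scheduled | No: measured, with no limit or hold |
| 6.4 | Check that eligibility criteria are met before using OPEN | No: stands under step 0, and no step-2 criteria exist for it to apply |
| 8.1, 8.2 | Dose changes for gastrointestinal events | No renal rule |
| 13.1 to 13.7 | Stopping rules, including known pregnancy | Stops drug for a known pregnancy; no test and no renal rule |
| 15.1.8 | Order open-label drug after re-registration, at least a week before the month-12 visit | No: timing of the order only |
| 15.1.9 | Creatinine before resuming after iodinated contrast | No: that situation only |

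**2. Age of the last required test at the first metformin dose.** Inputs: month-12 window 365 +/- 30 = 335 to 395 days (4.0); treatment starts at most 14 days after randomization (6.6.3); test windows of 7 and 30 days (3.3). Section 16.1.1 counts RPFNA months from randomization, while the schema footnote counts later follow-up from treatment start, so both origins are shown. Dosing at the month-12 visit is assumed.

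*Pregnancy test*
- Metformin arm: at most 7 + 14 = 21 days.
- Crossover, from randomization: 335 + 0 to 395 + 7 = 335 to 402 days.
- Crossover, from treatment start: 335 to 395 + 14 + 7 = 335 to 416 days.

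*Creatinine subject to a limit*
- Metformin arm: at most 30 + 14 = 44 days.
- Crossover, from randomization: 335 to 395 + 30 = 335 to 425 days.
- Crossover, from treatment start: 335 to 395 + 14 + 30 = 335 to 439 days.

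**3. A conditional case.** Re-registration and ordering can precede the month-12 chemistry. If drug were also handed over before that result was read, the newest creatinine would be from month 6. Month 6 is 182.5 +/- 21 = 161.5 to 203.5 days, so its age would be 335 - 203.5 = 131.5 to 395 - 161.5 = 233.5 days. The protocol does not instruct this sequence.

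**4. How many women.** With equal allocation, 96 / 2 = 48 are randomized to placebo. After 10% dropout, 48 x 0.9 = 43.2; the plan works with 44 per arm (16.1.1). Crossover uptake is not stated. Assuming 50% to 100% of 44 gives 22 to 44 women.

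**The case against.** The case for leaving the text alone is substantial.

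- **Clinical review coincides with crossover.** Month 12 already brings history, examination, chemistry, adverse events and concomitant medications, and an investigator may act on any of them. This stands: renal function is assessed, and what is absent is a stated limit and a requirement to read the result before release. Only the order is placed ahead of the visit, so the month-6 case above is a possibility and not the plan.
- **Pregnancy is not ignored.** Section 13.3 is not restricted by arm or phase. A reader might infer that a woman known to be pregnant could be started at step 2; Section 13.3 does not support that. What remains is undetected pregnancy.
- **Restarts are not treated more strictly.** A reader might set the rule that a woman "must not resume it until their creatinine level is satisfactory" beside crossover and conclude that a restart needs a creatinine check while a first dose does not. That comparison fails. Section 15.1.9 applies only after iodinated contrast and follows institutional practice. Sections 8.1 and 8.2.2 allow resumption after breaks for gastrointestinal toxicity with no creatinine condition.
- **Continuing metformin women also have no limit after entry.** True, and their entry tests are equally old at month 12. The distinction is that they were checked shortly before their own first metformin dose.
- **Low risk.** These are premenopausal women aged 25 to 55 who entered with acceptable creatinine and no serious comorbidity. This stands and keeps the point minor.
- **Unseen material.** The step-2 OPEN Enrollment Form and the model consent were not available for review and could contain such checks. The finding is therefore about the protocol text only.

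**Conclusion.** The point holds as a minor, safety-only improvement. Sections 4.0, 6.9 and 7.3 state no creatinine threshold and no repeat pregnancy test before a placebo woman's first metformin dose, although step 1 required both before study drug. At that dose the required pregnancy test is about 335 to 416 days old, against at most 21 days in the metformin arm. The last creatinine that had to meet a limit is 335 to 439 days old, against at most 44. At most 48 women are concerned, or about 44 after dropout.

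These figures assume equal allocation and first dosing at the month-12 visit; uptake is unknown. The documents give no rate of lactic acidosis or pregnancy in this population, so no rate of harm is claimed. Nor should a reader infer an effect on the trial's main result: the month-12 comparison precedes open-label treatment, and the power is untouched.

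**What to change.** Add to Sections 6.9 and 7.3:

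> *Open-label metformin is released to a patient crossing over from placebo only after her month-12 creatinine has been read and is at most 1.4 mg/dL and, for a woman of childbearing potential, a pregnancy test within 7 days before the first open-label dose is negative.*

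Add that pregnancy test to the Section 4.0 schedule for crossover women. Early ordering under 15.1.8 can stay, because the condition applies to release and not to procurement.

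Cost: a short amendment and at most 48 pregnancy tests. Creatinine needs no extra blood draw, since the month-12 panel is already scheduled. The first open-label dose may wait a few days for results, and a woman above the creatinine limit cannot start.
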